## **6.3. End of Treatment**

If a decision is made that the subject will permanently discontinue study treatment, the EOT visit should be conducted. If the EOT visit coincides with a regular study visit, the EOT evaluations will supersede those of that scheduled visit, and the data should be entered in the EOT visit in the eCRF. The subject should be encouraged to return for the follow-up visit.

## **6.4. Re-Treatment**

Subjects will be required to follow the re-treatment assessment schedule as outlined in [Table 5](#). Subjects are only permitted to restart treatment once if they experience recurrent GVHD after the taper of initial study treatment is completed. Subjects who complete re-treatment will repeat the EOT visit and subsequent safety, GVHD, and survival follow-up visits.

Corticosteroid tapering will be performed at the investigator's discretion. Investigators wishing to initiate a taper of itacitinib earlier than Day 180 may do so upon consultation with and approval from the sponsor's medical monitor.

## **6.5. Follow-Up**

### **6.5.1. Safety Follow-Up**

The safety follow-up period is the interval between the EOT visit and the scheduled follow-up visit, which should occur 30 to 35 days after the EOT visit (or after the last dose of study drug if the EOT visit was not performed). Adverse events and SAEs must be reported up until at least 30 days after the last dose of study drug, the date of the follow-up visit, or until toxicities resolve, return to baseline, or are deemed irreversible, whichever is longest.

If a subject withdrew from treatment due to reasons other than disease progression, GVHD staging and grading will be repeated at the safety follow-up visit.

### **6.5.2. Post-Treatment GVHD Follow-Up**

Subjects who completed study treatment or discontinued treatment for reasons other than GVHD progression will be followed every 28 days ( $\pm$  7 days) after the safety follow-up visit until any of the following occurs:

- GVHD progression.
- Initiation of a new anti-GVHD therapy.
- Relapse/recurrence of underlying hematologic disease.
- A maximum of 24 months from Day 1.

### **6.5.3. Survival Follow-Up**

Subjects who complete post-treatment follow-up, experience GVHD progression, or require a new anti-GVHD therapy should be contacted by telephone, email, or visit at least every 8 weeks ( $\pm$  7 days) after EOT to assess for new GVHD therapy and survival status until death, withdrawal of consent, or the end of the study, whichever occurs first.

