### **5.7.1. Withdrawal Criteria**

Subjects **must** be withdrawn from study treatment for the following reasons:

- The subject has experienced an unacceptable toxicity.
- Relapse of underlying malignancy or disorder.
- The subject is unable to tolerate itacitinib at a reduced dose specified for cohort.
- GVHD progression or lack of response. Requirement for additional systemic therapy, including corticosteroid doses greater than those used on Study Day 1, will qualify for GVHD progression.
- Further participation would be injurious to the subject's health or well-being, in the investigator's medical judgment.
- The subject becomes pregnant (may be applicable for Cohort 1).
- Consent is withdrawn.

- The study is terminated by the sponsor.
- The study is terminated by the local health authority, IRB, or IEC.

A subject **may** be withdrawn from study treatment as follows:

- If, during the course of the study, a subject is found not to have met eligibility criteria, then the medical monitor, in collaboration with the investigator, will determine whether the subject should be withdrawn from the study.
- If a subject is noncompliant with study procedures or study drug administration in the investigator's opinion, the sponsor should be consulted for instruction on handling the subject.

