#### **7.6.2. Chronic Graft-Versus-Host Disease Assessment**

Subjects will be assessed for signs and symptoms of cGVHD according to local institutional practice at screening, during the treatment phase, at EOT, and during re-treatment (if applicable) and follow-up as indicated in [Table 5](#). Definitive and possible manifestations of cGVHD should be assessed as per NIH consensus guidelines for cGVHD ([Jagasia et al 2015](#)).

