- Average and cumulative corticosteroid dose at Days 28, 56, 100, and 180; proportion of subjects who discontinue corticosteroids at Days 56 and 100.
- Proportion of subjects who discontinue immunosuppressive medication at Days 56 and 100.
- Incidence rate of aGVHD flares through Day 100.
- Incidence rate of cGVHD at Days 180 and 365.

[REDACTED]

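### Chronic GVHD is no longer assessed after the safety visit in children who stop treatment for GVHD progression, and no rule covers the gap, so the Day 180 and Day 365 cGVHD rates may be biased

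*Combined protocol and SAP*

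**What the plan says.** The endpoint is in Section 9.4.2: "Incidence rate of cGVHD at Days 180 and 365". Secondary analyses are run by cohort in the efficacy evaluable population, which Section 9.1 defines as everyone enrolled. Section 9.4.2 assigns cumulative incidence to nonrelapse mortality (NRM), relapse and relapse-related mortality, and Kaplan-Meier to failure-free and overall survival. It assigns no estimator to cGVHD and no rule for children whose status is unknown.

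Assessment of cGVHD is scheduled in Section 7.6.2 "at screening, during the treatment phase, at EOT, and during re-treatment (if applicable) and follow-up as indicated in" Table 5. Two kinds of follow-up visit carry it:

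- The safety visit, "which should occur 30 to 35 days after the EOT visit" (Section 6.5.1).
- The GVHD follow-up visits of Section 6.5.2, with restricted entry: "Subjects who completed study treatment or discontinued treatment for reasons other than GVHD progression will be followed every 28 days". They stop at progression, relapse, 24 months from Day 1, or "Initiation of a new anti-GVHD therapy".

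Section 5.7.1 widens the group that never enters GVHD follow-up: "Requirement for additional systemic therapy, including corticosteroid doses greater than those used on Study Day 1, will qualify for GVHD progression". After that, Section 6.5.3 applies: subjects "should be contacted by telephone, email, or visit at least every 8 weeks", and the contact serves "to assess for new GVHD therapy and survival status until death, withdrawal of consent, or the end of the study". cGVHD is not named there. Table 5 shows no cGVHD mark under survival follow-up, and the Amendment 2 change log likewise places follow-up cGVHD assessment at the safety and GVHD follow-up visits.

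**The concern.** Whether a child's cGVHD status is known at Days 180 and 365 depends on how that child's acute GVHD went. Children whose acute disease is controlled continue to be assessed. Those who progress or need new therapy drop out of cGVHD assessment while still alive, still in the study and still contacted every 8 weeks. This loss of ascertainment depends on outcome, so it cannot be assumed harmless.

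Because the plan does not say how such children enter the rate, a reader of the result could tell neither how large the error is nor which way it goes. Onset dates that are not collected prospectively may not be recoverable later.

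**Working it through.** The plan states no expected cGVHD rate or precision target, so there is no figure to reproduce. Three checks follow.

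**1. When the last scheduled assessment falls, for a child stopping for GVHD progression.**

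Inputs: end-of-treatment (EOT) visit 0 to 7 days after failure (the later side of the ± 7-day window in Table 5), and safety visit 30 to 35 days after EOT (Section 6.5.1).

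Last look = failure day + (0 to 7) + (30 to 35).

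- Failure at Day 28: from 28 + 0 + 30 = 58 to 28 + 7 + 35 = 70. Gap to Day 180: 180 − 70 = 110 to 180 − 58 = 122 days. Gap to Day 365: 365 − 70 = 295 to 365 − 58 = 307 days.
- Failure at Day 100: Day 130 to 142. Gaps: 38 to 50 days before Day 180, and 223 to 235 before Day 365.

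**2. How many children this could concern.**

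The documents do not give the share moved to survival contacts (f). As a proxy, take non-response. Adult first-line Day 28 response of 83.3% and 66.7% (Section 1.4.2) gives 16.7% to 33.3%. The 30% to 50% response of children to initial corticosteroids (Section 1.4) gives 50% to 70%.

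As an upper bound, suppose no case is captured after the move, cGVHD risk is 30% in both groups (assumed), and unassessed children count as event-free. Missed cases per cohort of 30 are 30 × f × 0.30:

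- f = 16.7%: 1.5
- f = 33.3%: 3.0
- f = 50%: 4.5
- f = 70%: 6.3

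**3. Bias by estimator, crediting assessments up to the safety visit.**

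Assumptions: constant hazards; cGVHD hazard λ = −ln(0.7)/365 per day (30% at one year without competing death) in children who stay; death hazard μ = 0.0005 per day; observation of moved children ending at Day 65.

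Incidence by day T in a group: I(T) = λ/(λ+μ) × [1 − exp(−(λ+μ)T)].

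With equal hazards, I(365) = 27.6% and I(65) = 6.1%. With f = 33.3%, the crude proportion is 0.667 × 27.6% + 0.333 × 6.1% = 20.4%, against a true 27.6%.

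Day 365 results for f = 33.3%, with moved children censored for both cGVHD and death at Day 65 in the last two columns:

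| Moved children, relative to the rest | True | Crude | Aalen-Johansen | 1 − Kaplan-Meier |
|---|---|---|---|---|
| Same cGVHD and death hazards | 27.6% | 20.4% | 27.6% | 30.0% |
| cGVHD hazard doubled | 34.1% | 22.3% | 29.0% | 31.4% |
| Death hazard 0.003 per day | 24.7% | 20.3% | 26.3% | 30.0% |

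With equal hazards, varying f from 16.7% to 50% moves the crude Day 365 figure from 24.0% to 16.8% (true 27.6%). At Day 180 the crude figure is 13.9%, 12.3% and 10.8% for f = 16.7%, 33.3% and 50% (true 15.4%).

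The crude proportion is too low in every row. A censored Aalen-Johansen estimate is right, too low or too high depending on hazards that the trial would not observe.

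**The case against.** A reader might infer that cGVHD is certain to be underestimated, and in the children most at risk of it. The documents do not support either part. No section says that acute progression or new therapy raises later cGVHD risk. Downward bias is certain only if unassessed children count as event-free, and the plan does not say that they will. With equal hazards, a censored cumulative incidence is unbiased.

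Ascertainment is also not absent. cGVHD is assessed on treatment, at EOT and at the safety visit, so a child who fails late has much of the year covered. The survival contact may be a visit, and its question on new GVHD therapy is not limited to acute disease, so some treated cGVHD would surface.

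Finally, this is one descriptive secondary endpoint, in cohorts of up to 30, with no hypothesis test. A telephone or email report also falls short of the NIH-consensus assessment that Section 7.6.2 calls for.

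All of this stands, and it limits the claim. It does not close the gap: for an early failure the scheduled assessments end months before either endpoint date, the therapy question records neither cGVHD status nor onset date, and the plan does not choose the estimator on which the direction of bias depends.

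**Conclusion.** The point holds in limited form. After EOT and the safety visit, cGVHD status is not systematically collected in children who stop for GVHD progression. In GVHD follow-up it ceases at progression, new anti-GVHD therapy or relapse. The Day 180 and Day 365 rates may therefore be biased.

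Under the assumed inputs, counting unassessed children as event-free understates Day 365 incidence by 27.6 − 20.4 = 7.2 percentage points, about a quarter in relative terms. Under censoring the sign cannot be known in advance. The length of the gap follows from the protocol's own visit schedule. The size of the bias rests on assumed cGVHD and death hazards and on non-response as a stand-in for the share moved, so it is an illustration and not a forecast. The reading of the Table 5 columns should be confirmed against the formatted table, although Sections 6.5.2 and 6.5.3 show the gap without it.

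Failure-free survival is little affected, because additional therapy for acute GVHD is already a failure event.

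**What to change.** - In Section 6.5.3 and the survival column of Table 5, add cGVHD status (yes or no since last contact) and onset date to the existing 8-weekly contact, through at least Day 365.
- Record whether each case was diagnosed at a visit or reported remotely, and show the two separately.
- In Section 9.4.2, estimate cGVHD by cumulative incidence with death as a competing event, in line with the method already named for NRM and relapse. State how relapse of the underlying disease and unknown cGVHD status are handled.

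The cost is a short question at a contact already scheduled and the matching eCRF fields, with no added visit. The downside is that remote reports are less detailed than an NIH-consensus assessment in person, which is why they should be flagged.

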## **6.6. Unscheduled Visits**

Unscheduled visits may be held at any time at the investigator's discretion, and appropriate clinical and laboratory measurements may be performed based on AEs or other findings. Any assessments performed at those visits should be recorded in the eCRF.

## **7. CONDUCT OF STUDY ASSESSMENTS AND PROCEDURES**

### **7.1. Administration of Informed Consent Form**

Valid informed consent must be obtained from the study subject (parent or legal guardian) before conducting any study-specific procedures using an ICF approved by the local IRB/IEC that contains all elements required by ICH E6 and describes the nature, scope, and possible consequences of the study in a form understandable to the study subject. Local and institutional guidelines for ICF content and administration must be followed; the original signed ICF must be retained by the head of the study site or its designee, and a copy of the signed ICF must be provided to the study subject. The informed consent process for each subject must be documented in writing within the subject source documentation.

### **7.2. Interactive Web Response Technology Procedure**

The IRT will be contacted to obtain a subject ID number when a subject enters the screening period. Upon determining that the subject is eligible for study entry, the IRT will be contacted to obtain study drug assignment. Additionally, the IRT will be contacted every 28 days to update study drug supply and at the EOT visit to record subject discontinuation from the study treatment. See Section [5.1.1](#) for additional information.

### **7.3. Demography and Medical History**

#### **7.3.1. Demographics and General Medical History**

Demographic data and a general medical history will be collected at screening.

#### **7.3.2. Disease Characteristics and Treatment History**

A disease-targeted medical and medication history including hematologic malignancy type, current aGVHD staging, date of diagnosis, sites of disease, prior anticancer therapy, ablation therapy, prophylaxis therapy, donor type, and other details related to the disease under study will be collected at screening.

### **7.4. Prior and Concomitant Medications and Procedures**

Prior and concomitant medications and procedures will be reviewed to determine subject eligibility. All prior and concomitant medications (including prophylactic and/or supportive care medications) and measures must be recorded in the eCRF, and any medication received or procedure performed within 30 days before enrollment (Day 1) and up to the safety follow-up visit will be recorded in the eCRF. The medication record will be maintained after signing the ICF to document concomitant medications, including any changes to the dose or regimen. Concomitant medications include any prescription, over-the-counter, or natural/herbal preparations taken or administered during the study period. Concomitant treatments and/or procedures that are required to manage a subject's medical condition during the study will also be recorded in the eCRF.

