### **4.4. Duration of Treatment and Subject Participation**

After signing the ICF, screening assessments will be completed over a period of up to 28 days. Subjects will receive study treatment in continuous 28-day cycles; this may include temporary treatment interruptions described in Section 5.6.3. Each subject enrolled in the study may continue to receive study treatment as long as benefit is being observed and/or treatment withdrawal criteria are not met. If the subject permanently discontinues study treatment (see Section 5.6.5 for details), the treatment period will end, and the subject will enter the follow-up period. The safety follow-up visit will occur 30 to 35 days after the last dose or EOT visit (whichever is later), and the post-treatment GVHD and survival follow-up periods will last until death or study withdrawal. Study participation is expected to average approximately 12 months per individual subject but may vary based on clinical outcomes.

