## **5.5. Treatment Compliance**

Treatment compliance with all study-related medications should be emphasized to the subject (parents or legal guardians) by the site personnel, and appropriate steps should be taken to optimize compliance during the study. Itacitinib compliance will be calculated, by the sponsor, based on the drug accountability documented by the site staff and monitored by the

sponsor/designee (tablet counts). Subjects (parents or legal guardians) will be instructed to bring all study-related medications with them to each study visit in order for site personnel to conduct tablet counts to assess study drug accountability. The drug accountability documentation will be used by the sponsor to calculate treatment compliance.

Although commercial supplies of corticosteroids will be used, dose changes and interruptions will also be documented in the medical record and monitored by the sponsor or its designee. As corticosteroid dose strengths and administration types will vary, compliance with corticosteroids will not be calculated.

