**Table 5: Schedule of Assessments**

Visit Day Item	Section	Screening	Treatment a											EOT d	Re-Treatment e	Follow-Up			
			-28 to -1	D1	D7	D14	D21	D28	D35	D42	D49	D56 b	D100	D180	D365 c	Safety f	GVHD g	Survival h	
Informed consent	7.1	X																	
Inclusion/exclusion criteria	3	X	X																
Contact IRT	7.2	X	X				X				X	X		X	X				
Demography/disease history	7.3	X																	
Prior/concomitant medications	7.4	X													X	X	X		
Supportive care medications	5.4	X													X	X	X		
AE assessment	7.5.1	X													X	X	X		
Physical examination	7.5.2	X	X	X	X	X	X	X	X	X	X	X		X	X	X			
Height and weight i	7.5.2	X	X j	X	X	X	X	X	X	X	X	X		X	X	X	X		
Vital signs	7.5.3	X	X j	X	X	X	X	X	X	X	X	X		X	X	X			
ECOG and Lansky scale performance status	7.5.4	X	X j	X	X	X	X	X	X	X	X	X		X	X	X			
12-lead ECG	9.5.4	X	X j												X				
aGVHD grading and response	7.6.1	X	X j												X	X	X	X	
cGVHD assessment	7.6.2	X													X	X	X	X	
Chimerism assessment/graft failure	7.6.3	X	X j																
PTLD assessment	7.6.4																		
Underlying disease relapse assessment	7.6.5	X	X j																
Dispense study drug	5.1			X				X				X			X		X		
Study drug compliance	5.5			X				X				X			X	X	X		
Steroid dose monitoring	5.3	X													X	X			
Survival follow-up	6.5.3																	X	
New GVHD therapies	6.5.2																		X

ECG = electrocardiogram; PTLD = post-transplant lymphoproliferative disorder.

a A ± 3-day window is permitted to facilitate scheduling during the treatment phase.

b After Day 56, visits will occur every 28 days and will include all Day 56 assessments.

c The Day 365 visit will also serve as the regularly scheduled visit occurring every 28 days after Day 56 (ie, Day 364).

d A ± 7-day window is permitted. A second EOT should occur if the subject restarts itacitinib and subsequently discontinues treatment.

e Re-treatment assessments occur every 28 days ± 3 days.

f 30 to 35 days after EOT.

g Every 8 weeks  $\pm$  7 days after EOT. Acute GVHD assessments are required every 28 days  $\pm$  7 days during survival follow-up for subjects who completed study treatment or discontinued early withdrew for reasons other than GVHD progression of GVHD.

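### The medication-recording window in Section 7.4 stops at the safety visit, so after an early end of treatment it falls short of the steroid landmarks (Days 56, 100, 180) and the immunosuppressant landmarks (Days 56, 100)

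*Combined protocol and SAP*

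**What the plan says.** **Recording window.** For the eCRF, Section 7.4 states that "any medication received or procedure performed within 30 days before enrollment (Day 1) and up to the safety follow-up visit will be recorded". Section 6.5.1 and Table 5 footnote f place the safety visit 30 to 35 days after EOT. Section 4.4 counts from the last dose or the EOT visit, whichever comes later.

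**Wider wording.** Section 7.4 also says: "Concomitant medications include any prescription, over-the-counter, or natural/herbal preparations taken or administered during the study period". Its closing sentence, repeated in substance in Section 5.7.4.1, requires eCRF entry of treatments needed to manage the child's condition over the study as a whole, with no end date.

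**Later contacts.** Section 6.5.2 sets 28-day visits for children who completed treatment or stopped for reasons other than GVHD progression, and names no dose recording. Section 6.5.3 sets contacts at least every 8 weeks "to assess for new GVHD therapy and survival status until death, withdrawal of consent, or the end of the study". Neither mentions steroid dose or continuing immunosuppressants.

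**Source data.** For corticosteroids, Section 5.5 says that "dose changes and interruptions will also be documented in the medical record and monitored by the sponsor or its designee". It gives no end date. Table 5 has a row called "Steroid dose monitoring", but its column marks cannot be read reliably in the available text, so nothing here rests on it.

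**Endpoints.** Section 9.4.2 lists "Average and cumulative corticosteroid dose at Days 28, 56, 100, and 180; proportion of subjects who discontinue corticosteroids at Days 56 and 100" and "Proportion of subjects who discontinue immunosuppressive medication at Days 56 and 100". It assigns the secondary analyses to the efficacy evaluable population, which Section 9.1 defines as everyone enrolled. It gives no rule for a child whose medication record ends before a landmark.

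**The concern.** The endpoints are fixed to days since the start of treatment, but the recording window is fixed to the end of treatment. When treatment ends early, the window can close before the landmark, while the child stays in the analysis population.

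The loss would not be random. Section 5.7.1 requires withdrawal for unacceptable toxicity, relapse, and GVHD progression or lack of response, and counts a need for more than the Day 1 steroid dose as progression. Section 5.6.4 lets itacitinib taper begin at Day 180 in complete or very good partial response, with earlier taper only on the medical monitor's approval. A child doing well is therefore normally still on drug through Day 180, and short records would come mostly from children doing badly. Average and cumulative steroid dose at Days 100 and 180 would then mainly describe children who stayed on itacitinib. If recorded doses were simply added up, the total would be too low for any child still on steroids after the record closed. Section 1.4 gives the potential to taper steroids as part of the reason for the trial, so these summaries will be read with interest even though they are descriptive.

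**Working it through.** The plan states no figure to reproduce. The check is calendar arithmetic.

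Inputs:
- x = day of the EOT visit (Day 1 = first dose), taken as no earlier than the last dose.
- Recording ends at the safety visit, between x + 30 and x + 35 (Sections 7.4, 4.4, 6.5.1).
- Landmarks T = 28, 56, 100, 180 (Section 9.4.2). Day 28 and Day 180 apply to steroid dose only.

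Formulas:
- The record never reaches T if x + 35 < T, that is x ≤ T − 36.
- It is certain to reach T if x + 30 ≥ T, that is x ≥ T − 30.
- In between, it depends on the date of the safety visit.

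| Landmark T | Never reached if EOT is on or before | Certain if EOT is on or after |
|---|---|---|
| 28 | no such day (earliest end is 1 + 30 = Day 31) | Day 1 |
| 56 | 56 − 36 = Day 20 | 56 − 30 = Day 26 |
| 100 | 100 − 36 = Day 64 | 100 − 30 = Day 70 |
| 180 | 180 − 36 = Day 144 | 180 − 30 = Day 150 |

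By day of last dose, d: Table 5 footnote d allows 7 days around the EOT visit. If that visit may fall as late as d + 7, the record can run to at most d + 7 + 35 = d + 42. It never reaches T if d + 42 < T, which gives d ≤ 13, 57 and 137 for Days 56, 100 and 180.

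Examples:
- EOT on Day 14: the record ends on Days 44–49. Days 56, 100 and 180 are all missed.
- EOT on Day 28: the record ends on Days 58–63. Day 56 is reached. Unrecorded to Day 100: 100 − 63 = 37 to 100 − 58 = 42 days. Unrecorded to Day 180: 180 − 63 = 117 to 180 − 58 = 122 days, or 117/180 = 65.0% to 122/180 = 67.8%.
- EOT on Day 100: the record ends on Days 130–135. Only Day 180 is missed.

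The endpoints are not hit equally. Cumulative dose needs every day up to the landmark, so a short record leaves it incomplete for any child whose steroids continue. Discontinuation needs only status: a stop date recorded before the safety visit still classifies the child at Days 56 and 100 unless the drug is restarted. A restart given as new GVHD therapy would be picked up at the contacts in Section 6.5.3.

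**The case against.** The strongest objection is that the plan does require later recording. The closing sentence of Section 7.4 and Section 5.7.4.1 impose an eCRF duty not tied to the safety visit, and both are worded as additional to what comes before. Section 5.7.4.1 refers to Section 5.4, which names systemic GVHD prophylaxis drugs, so immunosuppressants plausibly fall under it. This stands in part. A reader might infer that the later landmarks can never be reached after an early stop, and the documents do not support that: they contain two recording rules. However, only one rule has an explicit end point, and neither Section 6.5.2 nor Section 6.5.3 lists the data that the wider rule would need. Sites could follow either.

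Other inferences go too far:
- That steroid doses are kept out of the eCRF. Section 5.5 says they are also documented in the medical record; it does not exclude the eCRF.
- That the adult study gives the scale. Section 1.4.2 reports 15 of 29 adults (51.7%) stopping for an adverse event, but in mixed steroid-naive and steroid-refractory patients at two doses, some with fatal events, and without timing. It does not show how many children would outlive their record.
- That the primary endpoint loses its Day 28 staging after an early stop. Section 7.6.1 sets weekly grading for 8 weeks from study start, not from time on drug. Read that way, Day 28 is staged. Its later paragraph, Section 6.5.2 and Table 5 footnote g (which opens with an 8-week interval and then gives 28 days) need reconciling, but they do not establish a gap.

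The eCRF Completion Guidelines (Section 5.1.1) or the study reference manual (Section 6) may settle the recording end date. If so, the protocol should agree with them.

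**Conclusion.** The point holds as a conflict between the window stated in Section 7.4 and the landmarks in Section 9.4.2. A site that follows the stated window has no record to Day 56, 100 or 180 for EOT on or before Day 20, 64 or 144; coverage is certain only from Day 26, 70 or 150. Later steroid-dose summaries would be selectively incomplete and lean towards children who stayed on itacitinib. The steroid and immunosuppressant discontinuation proportions are affected less.

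This rests on three assumptions: the safety visit takes place on schedule, the stated window rather than the wider wording governs, and the child is alive and consenting after the record closes. The number of children affected cannot be derived from the documents. Steroid dose at Day 28 is untouched, and Sections 9.2 and 9.3 rule out formal tests, so no error rate or power is at stake. The change is worth making because it is cheap and because doses not captured during the trial may be hard to recover later.

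**What to change.** 1. In Sections 7.4, 6.5.2 and 6.5.3, and in the Table 5 rows for medications and steroid monitoring, reconcile the two recording rules. State that systemic corticosteroid dose is recorded to Day 180, and immunosuppressant use to Day 100, for all living, consenting children whether or not itacitinib continues.
2. Collect these data at the existing GVHD and survival contacts, with the medical record as the source. The first contact on or after each landmark closes that record.
3. In Section 9.4.2, report by cohort how many children have an incomplete record at each landmark.
4. As a clarification only, align Section 7.6.1, Section 6.5.2 and Table 5 footnote g on off-drug staging. Confirm that weekly staging from study start, including Day 28, applies to children who stop itacitinib early for reasons other than GVHD progression.

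The cost is an added eCRF field and amendment wording, with no new visits for the dose data. The drawback is that doses gathered between 8-weekly contacts are less exact than doses recorded at visits, which is why the medical record rather than recall should be the source.
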